## Statistical Analysis Plan for CLM-INS-004

Version: Final 2.0

Date: 9th September 2022

To assess safety of patients using the digital sleep diary.	Numbers of AEs and SAEs.	Participants will be asked to report any AEs experienced during the three-week observational period at Day 21 in a telephone consultation with the study team.
To determine associations between severity of insomnia and clinical or treatment characteristics of breast cancer patients.	Assessment of insomnia prevalence, severity, and quality of life in subgroups based on clinical/treatment characteristics including breast cancer stage, treatment regime, prior chemotherapy, and baseline insomnia severity.	Performed on data collected at Stage 1 and Stage 2.

## 1.2. Study Design

This is a two-stage prospective observational study of insomnia in patients with breast cancer. This is designed as a remote observational study to be conducted in the community with no participant visits required to investigational site. However, there will be the option to recruit participants in-person, if required.

In the first stage of the study, eligible breast cancer patients consenting to participate will complete the ISI scale to determine prevalence of insomnia. Additional data will be collected from participants and is described in the Assessment Schedule (Table 1). Participants scoring  $\geq 8$  on the ISI, will then be assessed for eligibility to Stage 2.

Following stage 1, eligible participants will be invited to consent to taking part in Stage 2 of the study. Those consenting will be asked to download and complete a daily digital sleep diary on their smartphone over a three-week observation period. At the end of the three-week observation period, participants will be asked to complete a series of questionnaires and additional procedures as outlined in the Assessment Schedule (Table 1).

The digital sleep diary comes in the form of a patient-facing mobile phone application. All daily sleep diary data will be collected in the app.

## Statistical Analysis Plan for CLM-INS-004

Version: Final 2.0

Date: 9th September 2022**Table 1 Assessment Schedule**

Assessment/ Procedure	Stage 1		Stage 2			
	Screening (-14 days)	Day 0	Screening (-28 days) 	Day 0	Days 1-21	Day 21 (+8 days)
Stage 1:						
Informed Consent  for Stage 1 & Registration	x					
ISI 		x				
EQ-5D-5L 		x				
FACT-ES 		x				
Demographics 		x				
Sleep History 		x				
Stage 2:						
Informed Consent for Stage 2 			x			
Review Eligibility Criteria			x			
Cancer Medical History				x		
Current Cancer Treatment				x		
Current Co-Morbidities				x		
Digital Diary Download 				x		
Daily Sleep Diary Entry 					x	
ISI 						x
EQ-5D-5L 						x
FACT-ES 						x
UEQ 						x
Adverse Events 						x

 Where possible will be online remote eConsent but can be completed in clinic (online/paper). Participant completes online questionnaire (paper questionnaires will be available for clinic use). Participants completes on their own smartphone. AEs will be collected at follow-up telephone consultation at Day 21 (+8 days). Stage 2 Consent should occur no later than 28 days post Stage 1 Consent, however ideally this would occur as soon as possible after consent for Stage 1 has been provided.**1.2.1. Sample Size Considerations**

The sample size required for Stage 1 is based on an assumed prevalence of insomnia of 44% in breast cancer patients. A sample size of 267 participants is required for estimating the expected prevalence rate with 5% absolute precision and 90% confidence or 6% absolute precision and 95% confidence.

## Statistical Analysis Plan for CLM-INS-004

Version: Final 2.0

Date: 9th September 2022

The target for Stage 2 is for approximately 100 participants to complete the study, to provide sufficient data to assess the secondary objectives. With an assumed prevalence of 44% and a 20% drop out rate, then 285 participants in Stage 1 would give an expected 125 eligible participants for Stage 2 with 100 participants assumed to complete the 3-week observation period.

Therefore, the study will aim to recruit a minimum of 285 patients into Stage 1 to cover the sample size requirements for Stage 1 and Stage 2.

If the actual prevalence rate is higher than the assumed rate or the drop-out rate is lower, then the study may recruit less patients to achieve the desired 100 patients in stage 2 or the study could continue to the original recruitment target of 285 and achieve > 100 patients in stage 2. This decision will be driven by availability of patients and desired study reporting timelines ensuring the minimum target is reached.

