### 2.2. Definitions of Analysis Sets

The following analysis sets will be used in the statistical analyses and reporting of study data.

- Stage 1 analysis set will include all participants who consented to stage 1, are eligible for the study and have evaluable data for at least one of the questionnaires (ISI, EQ-5D-5L or FACT-ES).
- Stage 2 analysis set will be a subset of the Stage 1 analysis set and will include eligible Stage 1 participants who scored  $\geq 8$  on their baseline ISI questionnaire and consented to stage 2. Note if a patient consents to Stage 2 but does not provide **any** stage 2 data (e.g., questionnaire/sleep data) then they will be excluded from the stage 2 analysis set.

Statistical Analysis Plan for CLM-INS-004

Version: Final 2.0

Date: 9th September 2022

Note, listings will generally be based on the stage 1 analysis set with an indicator for patients who also entered into stage 2, with the exception of the cancer history, cancer treatment, co-morbidities, sleep diary, AE and UEQ listings which will be based on the stage 2 analysis set since these are only completed for stage 2 patients.

If a participant does not enroll in the digital diary (i.e., does not even download the app) but completes the UEQ, then data from the UEQ will not be included in the reporting of the data.

Percentages will generally be derived based on the analysis set N as the denominator, unless stated otherwise. Where there is missing data, % may be derived based on those within the analysis set who have evaluable data. Where applicable missing categories will be included to show the number of patients with missing data for the relevant endpoint.

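### The 125 called eligible for Stage 2 is only the expected count with ISI ≥8, so the stated yield of 100 completers is too favourable; a lesser point is that SAP 1.2.1 lets Stage 1 stop below 285 with no numbered floor

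*SAP*

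**What the plan says.** **Stage 2 yield.** SAP 1.2.1 and protocol 10.1 assume 44% prevalence and 20% drop-out, and state that "285 participants in Stage 1 would give an expected 125 eligible participants for Stage 2 with 100 participants assumed to complete" the three-week period. Insomnia is defined throughout as an ISI total of 8 or more. SAP 1.2 then places two further steps after that threshold. Patients reaching it "will then be assessed for eligibility to Stage 2", and after that "eligible participants will be invited to consent to taking part in Stage 2 of the study". Protocol 6.1 and 6.2 give the other Stage 2 criteria: onset or worsening of sleep problems since the cancer diagnosis, a usable smartphone, and no incompatible co-morbidity, sleep apnoea, regular shift work or breast feeding. Protocol 7.4 makes the Stage 2 consent separate from that for Stage 1.

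**Stage 1 size.** For the primary endpoint, SAP 1.2.1 says: "A sample size of 267 participants is required for estimating the expected prevalence rate with 5% absolute precision and 90% confidence", or alternatively 6% at 95% confidence. It then says "the study will aim to recruit a minimum of 285 patients into Stage 1", as protocol 10.1 does, and protocol 7.2 ends recruitment at 285. The next SAP paragraph covers higher prevalence or lower drop-out: "then the study may recruit less patients to achieve the desired 100 patients in stage 2", or recruitment may continue to 285. It adds: "This decision will be driven by availability of patients and desired study reporting timelines ensuring the minimum target is reached". SAP Section 4 lists four changes from the protocol, and this is not one of them.

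**The concern.** A count labelled eligible should already be net of the eligibility criteria, and a count of patients starting Stage 2 should also be net of consent. The documents give no rate for either step, and the arithmetic leaves no room for them. A reader planning the follow-on trial named in protocol section 2 would take from this an entry rate into Stage 2 that the plan has not justified.

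The lesser issue is that the size of the primary sample may be governed by a Stage 2 count and by timelines. The one safeguard refers to a minimum target without giving a number or a stage. Three figures could be meant:

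- 285, the only figure that SAP 1.2.1 calls a minimum, although this would cancel the permission to recruit fewer;
- 267, the stated Stage 1 requirement;
- 100 in Stage 2.

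Only the third leaves the primary endpoint without a floor.

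**Working it through.** **Inputs.** Prevalence 44%, drop-out 20%, Stage 1 sizes 267 and 285, and a Stage 2 target of about 100 completers (SAP 1.2.1, protocol 10.1). The cited prevalence range is 19-69% (protocol 10.1). The share *q* of ISI ≥8 patients who meet the other criteria and consent is not in the documents. It is an assumption here and is shown over a range.

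**1. Reproducing the plan.** Using n = z²p(1−p)/d² with p = 0.44:

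- 90% confidence, d = 0.05: 1.645² × 0.44 × 0.56 / 0.05² = 266.7, so 267.
- 95% confidence, d = 0.06: 1.96² × 0.44 × 0.56 / 0.06² = 262.9, so 263, which 267 covers.
- Stage 2: 100 / 0.8 = 125, and 125 / 0.44 = 284.1, so 285. Forward, 285 × 0.44 = 125.4 and 125.4 × 0.8 = 100.3.

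The stated figures all reproduce. The last line shows that 125 is the ISI ≥8 count with nothing else deducted.

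**2. Stage 2 yield with *q* included.** Completers = 285 × 0.44 × q × 0.8 = 100.32q.

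- Rate needed for 100 completers: q = 100 / 100.32 = 0.997.
- q = 0.9: 112.9 entering, 90.3 completing.
- q = 0.8: 100.3 entering, 80.3 completing.

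These figures count the 20% drop-out separately, after entry.

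**3. Stage 1 size if the minimum target means 100 Stage 2 completers.** Take n = 100 / (p × (1 − drop-out) × q), rounded up and capped at 285, with 95% half-width 1.96√(p(1−p)/n).

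- q = 1, 20% drop-out, p = 0.50: n = 100 / (0.50 × 0.8) = 250, half-width 6.2 points.
- q = 1, 20% drop-out, p = 0.69: n = 100 / (0.69 × 0.8) = 181.2, so 182, half-width 6.7 points.
- q = 1, 10% drop-out, p = 0.44: n = 100 / (0.44 × 0.9) = 252.5, so 253, half-width 6.1 points. Lower drop-out alone is therefore enough to take n below 267.
- At q = 1 and 20% drop-out, n falls below 267 once p exceeds 100 / (267 × 0.8) = 46.8%.

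Largest half-width over 44-69% prevalence, in percentage points (each peak lies near 67% prevalence):

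| Drop-out | q = 1 | q = 0.81 (assumed) |
|---|---|---|
| 20% | 6.75 | 6.1 |
| 10% | 7.2 | 6.4 |
| 0% | 7.5 | 6.8 |

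The planned figure is 6. Keeping 285 gives 5.8 at 44%.

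**4. What a floor of 267 gives.** At 44% the half-width is 1.96√(0.44 × 0.56 / 267) = 5.95 points by the normal approximation. On the Clopper-Pearson interval that SAP 3.2.1 will report, 117 of 267 gives 37.8% to 50.0%, a half-width of about 6.1.

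**The case against.** Several objections carry weight.

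- **The two points pull against each other.** Early stopping costs most precision when every ISI ≥8 patient enters Stage 2, which is what the first point doubts. At q = 0.81 and 20% drop-out the largest half-width is only 6.1. This stands, and it is why the early-stop point is minor.
- **The early-stop effect is conditional.** It needs higher prevalence or lower drop-out, a decision to stop, and one reading out of three. The statement that 267 is required can fairly be taken to govern the safeguard. The text does not say so, however, and in a paragraph about Stage 2 yield the reading as 100 is also natural.
- **The consequences are descriptive.** No test or decision rule depends on either figure, and the reported interval will show whatever precision was reached. This stands.
- **The 20% might already include refusals.** It could include non-consent, since it is not defined. It cannot readily include ineligibility, because it is applied to patients already called eligible.
- **A floor may come too late.** Recruitment was planned to end by January 2022 (protocol 7.1) and SAP 2.0 is dated September 2022. The documents do not say whether recruitment had closed, so the remedy has to cover both cases.

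A reader might also infer that protocol 10.2 contradicts the 44%, because it forecasts 7-8 of 15 per week as eligible where 15 × 0.44 = 6.6. That forecast is expressly approximate and the gap is under one patient a week. It does not support a separate finding.

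**Conclusion.** The main point holds. The 125 in SAP 1.2.1 and protocol 10.1 is an ISI ≥8 count presented as an eligible count. The chain from 285 to 100 completers holds only at a joint eligibility-and-consent rate of about 99.7%. At assumed rates of 0.9 and 0.8 the expected completers are about 90 and 80. The true rate is unknown from the documents. Stage 2 has an approximate target and descriptive outcomes, so this is a misstated yield. A reader might infer that Stage 2 is too small to meet its objectives, but no precision or test is tied to 100.

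The minor point holds as a matter of text: an unlisted departure from protocol 7.2 and 10.1 with an unnumbered safeguard. A reader might infer that the primary endpoint has lost its sample-size protection. The documents do not establish that, because two of the three readings keep Stage 1 at 267 or more. On the third, the loss in the cases examined is at most about 1.5 points beyond the planned 6 (7.5 − 6, at 0% drop-out with every ISI ≥8 patient entering). The 6.75 figure should not be quoted as a ceiling, since it holds only at 20% drop-out and SAP 1.2.1 is also triggered by lower drop-out. Nor is bias the main worry: a simulation of stopping at 125 ISI ≥8 cases shifted the prevalence estimate by about +0.2 points.

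**What to change.** **Stage 2 yield (main).** In SAP 1.2.1, and in protocol 10.1 if it is amended, relabel 125 as the expected number with ISI ≥8. Restate expected Stage 2 entrants and completers under an explicit eligibility-and-consent assumption, preferably over a range. Say whether the 20% drop-out includes non-consent.

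**Stage 1 stopping (minor).** List the departure from protocol 7.2 and 10.1 in SAP Section 4. Then:

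- If recruitment is still open, replace the unnumbered safeguard with a floor of 267 Stage 1 participants with an evaluable ISI total score, whatever the Stage 2 count. The ISI condition is needed because SAP 2.2 admits participants who "have evaluable data for at least one of the questionnaires", so the Stage 1 analysis set can include people without an ISI score.
- If recruitment has closed, report the Stage 1 number reached, why recruitment stopped and the precision achieved. SAP 3.1.1 already covers the numbers consenting and in each analysis set, but not the reason for stopping.

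The cost is wording. No patients are needed beyond the planned 285, and the stated Stage 2 yield will look less favourable.

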## 2. ANALYSIS AND REPORTING CONSIDERATIONS

### 2.1. General Considerations

Statistical analysis will be performed using SAS® software. Continuous variables will be summarized using the mean, the standard deviation [SD], median, 25th and 75th percentiles, minimum value, and maximum value. Categorical variables will be summarized using frequency counts and percentages. Data will be listed in data listings.

Where applicable, 95% confidence intervals (CIs) will be presented.

The tables, listing and figures will be developed as a separate standalone document from the SAP. The document will provide templates of the outputs to be provided following database lock based on the summaries detailed in the SAP. All data will be listed, in addition to the summaries outlined in the SAP

### 2.2. Definitions of Analysis Sets

The following analysis sets will be used in the statistical analyses and reporting of study data.

- Stage 1 analysis set will include all participants who consented to stage 1, are eligible for the study and have evaluable data for at least one of the questionnaires (ISI, EQ-5D-5L or FACT-ES).
- Stage 2 analysis set will be a subset of the Stage 1 analysis set and will include eligible Stage 1 participants who scored  $\geq 8$  on their baseline ISI questionnaire and consented to stage 2. Note if a patient consents to Stage 2 but does not provide **any** stage 2 data (e.g., questionnaire/sleep data) then they will be excluded from the stage 2 analysis set.

Statistical Analysis Plan for CLM-INS-004

Version: Final 2.0

Date: 9th September 2022

Note, listings will generally be based on the stage 1 analysis set with an indicator for patients who also entered into stage 2, with the exception of the cancer history, cancer treatment, co-morbidities, sleep diary, AE and UEQ listings which will be based on the stage 2 analysis set since these are only completed for stage 2 patients.

If a participant does not enroll in the digital diary (i.e., does not even download the app) but completes the UEQ, then data from the UEQ will not be included in the reporting of the data.

Percentages will generally be derived based on the analysis set N as the denominator, unless stated otherwise. Where there is missing data, % may be derived based on those within the analysis set who have evaluable data. Where applicable missing categories will be included to show the number of patients with missing data for the relevant endpoint.

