3.4 Secondary endpoints/outcomes

Secondary evaluation criteria:

- i. Insomnia Severity (ISI): Severity of insomnia will be determined at screening/baseline (all screened patients in Stage 1 of the study) and following the 3-week observational period (all patients enrolled in Stage 2 of the study), based on the total ISI score obtained by summing the seven items to provide a score from 0-28 categorised as follows:
 - 0–7 = No clinically significant insomnia
 - 8–14 = Subthreshold insomnia
 - 15–21 = Clinical insomnia (moderate severity)
 - 22–28 = Clinical insomnia (severe)
- ii. Sleep efficiency (Sleep diary): Participants' responses collected from the sleep diary will be used to calculate sleep efficiency during the observational period: Sleep efficiency = Total sleep time/Total time in bed.
- iii. Quality of Life (EQ-5D-5L): Data from the EQ-5D-5L self-classifier, which includes five dimensions (mobility, self-care, daily activities, pain/discomfort, and anxiety/depression) will be used to calculate an index value as a measure of the participant's health, both at screening/baseline (all screened patients) and following the observational period (all enrolled patients).
- iv. Quality of Life (FACT-ES): Data from the FACT-ES, which includes five subscale domains (physical well-being, social/family well-being, emotional well-being, functional well-being and endocrine symptom subscale), will be used to calculate an index value as a measure of the participant's health, both at screening/baseline (all screened patients) and following the observational period (all enrolled patients).
- v. Compliance of data entry into the digital sleep diary: Compliance will be assessed as the proportion of participants completing the digital sleep diary on at least 17 out of 21 days.
- vi. User Experience Questionnaire (UEQ): Patient experience, feedback, and satisfaction rating from use of digital diary. This will be assessed once (at the end of study), using the UEQ designed to evaluate the participant's experience of the digital sleep diary. Participants who withdraw from the study will be offered the questionnaire.
- vii. Adverse events: The numbers of AEs and serious adverse events (SAEs) will be determined. Participants enrolled in Stage 2 will report AEs at the conclusion of the three-

week observational period in a telephone consultation with the clinical study team. Any relationship with the AE/SAE to the usage of the digital sleep diary will be recorded.

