8.5 Adherence to the digital sleep diary and study questionnaires

As compliance of data entry into the digital sleep diary is a secondary outcome, adherence to the digital sleep diary will not be monitored during the three-week study period. Adherence to the enrolment procedure required for downloading and setting up the digital sleep diary on participants smartphones will be assessed remotely by Closed Loop Medicine. If digital sleep diary has not been downloaded within three days of the participant receiving instructions to do so, the eCRF will send a reminder by email or text. If after another three days, the digital sleep diary has not been downloaded the clinical study team will attempt to call the participant to remind participant to download the app and determine if they require any assistance doing so. Compliance of data entry into the digital sleep diary during three-week study period will be assessed at the end of the three-week study period by Closed Loop Medicine.

Questionnaire adherence will be monitored by the clinical study team throughout the study period. Questionnaire reminders, at baseline and end of study, will be sent by email or text message to participants by the Qualtrics^{XM} platform. Reminder email or text messages will be sent up to three times, three days apart. If the end of study questionnaire set remains uncompleted, the clinical research team will remind the participant to complete the questionnaire during remote telephone consultation at day 21.

Non-compliance to the protocol study procedures will be documented by the investigator in the participant study files and site deviation log.

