## 1.1. Study Objectives

Objectives	Outcome Measures	Timepoint(s) of evaluation of this outcome measure (if applicable)
Primary Objective:		
Prevalence of insomnia in a cohort of breast cancer patients.	Proportion of screened patients with insomnia defined as a total ISI score of 8 or more.	Stage 1 assessment of insomnia severity performed at baseline via administration of the ISI for all participants enrolled in Stage 1.
Secondary Objectives:		
To assess insomnia severity in breast cancer patients experiencing insomnia (ISI $\geq$ 8)	Proportion of participants in each ISI category of insomnia severity based on the ISI total score.	Assessment of insomnia severity will be performed at baseline/screening and day 21 via administration of the ISI for all participants enrolled in Stage 2.
To assess sleep efficiency in breast cancer patients experiencing insomnia (ISI $\geq$ 8)	Sleep efficiency defined as total sleep time relative to total time in bed.	Sleep efficiency will be assessed via the digital sleep diary completed daily over the 3-week observation period for all participants enrolled in Stage 2.
To assess quality of life in breast cancer patients experiencing insomnia (ISI $\geq$ 8).	Data from the EQ-5D-5L questionnaire which includes five dimensions (mobility, self-care, daily activities, pain/discomfort, and anxiety/depression), will be used to calculate a measure of the participant's health.	Quality of life will be evaluated at baseline on all eligible participants in Stage 1 and at Day 21 on all participants enrolled in Stage 2.
To assess quality of life in breast cancer patients experiencing insomnia (ISI $\geq$ 8).	Data from the FACT-ES questionnaire which includes five subscale domains (physical well-being, social/family well-being, emotional well-being, functional well-being, and endocrine symptom subscale), will be used to calculate an index value as a measure of the participant's health.	Quality of life will be evaluated at baseline on all eligible participants in Stage 1 and at Day 21 on all participants enrolled in Stage 2.
To assess compliance of data entry into the digital sleep diary.	Compliance will be assessed as the proportion of participants completing the digital sleep diary on at least 17 out of 21 days.	Compliance will be calculated for each participant completing the three-week observational period in Stage 2.

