## Statistical Analysis Plan for CLM-INS-004

Version: Final 2.0

Date: 9th September 2022

- Quality of sleep rating (rated 1 (awful) to 10 (excellent))

Compliance of entry into the digital sleep diary will be assessed as follows:

- Entry compliance: Number and % of patients who used the diary at least once (i.e entered at least one data point into the diary)
- Completion compliance: Number and % of participants completing the digital sleep diary on at least 17 out of 21 days.
- Overall diary compliance rate derived as:
  - (number of days sleep diary completed/21)\*100%

Sleep diary data will be listed and summarized based on the stage 2 analysis set only. If any sleep variables cannot be determined at a timepoint (due to partial/missing data) then relevant variables will be considered missing at the affected timepoint(s) and excluded from the relevant data summaries.

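### Diary compliance may leave out Stage 2 consenters who never engaged: add a denominator of all eligible consenters and close the definition of Stage 2 data

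*SAP*

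**What the plan says.** Protocol 3.4, item v, defines the endpoint: "Compliance will be assessed as the proportion of participants completing the digital sleep diary on at least 17 out of 21 days". It does not limit participants to those who returned something. Item viii of the same section describes the full analysis set as everyone enrolled, although that sentence concerns subgroup analyses of other criteria.

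SAP 3.3 splits compliance into three measures. The first is new in the SAP: "Entry compliance: Number and % of patients who used the diary at least once". The second is the protocol's 17-of-21 rule, and the third is days completed divided by 21. The section closes with "Sleep diary data will be listed and summarized based on the stage 2 analysis set only".

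SAP 2.2 defines that set. Membership needs eligibility, a baseline ISI of at least 8 and Stage 2 consent. A consenter with none of the required data is then removed: "stage 2 data (e.g., questionnaire/sleep data) then they will be excluded from the stage 2 analysis set". On denominators the section says "Percentages will generally be derived based on the analysis set N as the denominator, unless stated otherwise", and it also allows percentages among those with evaluable data. It foresees one kind of non-user, "If a participant does not enroll in the digital diary (i.e., does not even download the app) but completes the UEQ", and for that person drops only the UEQ answers.

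SAP 3.1.1 reports how many signed each consent and the size of each analysis set. SAP section 4 lists a clarification of the analysis sets as a change from the protocol, without mentioning any effect on compliance.

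**The concern.** For most outcomes it is reasonable to leave out people with no data. Compliance is different, because giving no data is the failure being measured. If those people leave the denominator, the rate answers how well the diary was kept by those who gave something, not how many of those who agreed to keep it did so. The second question is closer to the protocol's wording, and no planned compliance output addresses it.

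The documents expect some consenters not to engage. Protocol 7.4.3 and 8.5 plan reminders and a telephone call for people who have not downloaded the app, and SAP 2.2 has its rule for non-downloaders.

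Entry compliance is the most exposed measure, because using the diary once is itself a way into the set.

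The size of the exclusion turns on an open example. Two analysts following the same SAP could form different sets and publish different rates.

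**Working it through.** **The plan's own figures.** SAP 1.2.1 assumes 285 in Stage 1, 44% prevalence and 20% drop-out.
- 285 × 0.44 = 125.4, taken as 125 eligible for Stage 2.
- 125 × 0.80 = 100 completing.

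These reproduce. The 125 are eligible, not consenting, so using N = 125 consenters below is an assumption.

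**Who is removed under each reading of Stage 2 data**

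| Counts as Stage 2 data | Consenter who never uses the diary and returns no questionnaire |
|---|---|
| Questionnaire or diary data only | Removed |
| Also what the participant reports in the adverse event call (Protocol 7.4.5) | Stays if the call is answered |
| Also site-entered cancer history, treatment and co-morbidities (Protocol 7.4.4) | Stays in nearly every case |

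The rule speaks of a patient who does not provide data, which leans towards the first row. The second and third rows are not ruled out.

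**Formulas.** Let u = consenters who used the diary at least once, q = those who returned questionnaires only, k = those with no Stage 2 data, and N = u + q + k. Neither k nor q is in the documents.
- Entry compliance: u/(u + q) on the set; u/N on all consenters.
- Completion and mean overall compliance: the k people add nothing to the numerator, so the rate on the set equals the all-consenter rate × N/(N − k).

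**Completion and mean overall, N = 125**
- k = 0: 125/125 = 1.00
- k = 5: 125/120 = 1.04
- k = 10: 125/115 = 1.09

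With N = 110 (also assumed), k = 5 gives 110/105 = 1.05 and k = 10 gives 110/100 = 1.10.

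To put this in percentage points, suppose for illustration that 80 people meet the 17-of-21 rule. The all-consenter rate is 80/125 = 64.0%. On the set it is 80/120 = 66.7% at k = 5 and 80/115 = 69.6% at k = 10.

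**Entry compliance, N = 125**

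| k | q | On the set | On all consenters |
|---|---|---|---|
| 5 | 0 | 120/120 = 100.0% | 120/125 = 96.0% |
| 10 | 0 | 115/115 = 100.0% | 115/125 = 92.0% |
| 5 | 5 | 115/120 = 95.8% | 115/125 = 92.0% |
| 10 | 5 | 110/115 = 95.7% | 110/125 = 88.0% |

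Entry compliance is therefore 100% by construction only when q = 0.

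**Start of the 21 days.** The 17-of-21 rule allows 21 − 17 = 4 blank days. Someone who leaves five days blank after download and then enters daily scores 16/21 counted from download. The same person could score 21/21 counted from the first entry, but only if app access also runs three weeks from that entry. Protocol 11.2 closes access at the end of the three weeks without saying when they begin.

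**The case against.** The strongest reply is that the exclusion may be empty. Staff enter clinical data for each Stage 2 consenter, and participants themselves report adverse events by telephone. If either counts, nearly everyone stays in. This stands, and it is why the point is conditional.

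Second, an all-consenter rate can largely be rebuilt. Disposition gives the consent count and the set size, and SAP 3.3 gives numbers with percentages for entry and completion. The mean overall rate can be rescaled too, since excluded people add zero days. This mostly stands. The rebuilt figure is only approximate, because the set also requires eligibility, so the gap between consents and set size can mix ineligible and no-data consenters. SAP 3.1.1 plans reasons for withdrawal but not for exclusion from the set.

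Third, non-users are not ignored. Those who return a questionnaire appear to remain in the set and count against compliance. That is correct and limits the effect to people who return nothing. Entry compliance is also a SAP addition, not the protocol's endpoint.

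Three stronger readings are tempting but not supported:
- A reader might infer from the timepoint column of SAP 1.1 ("Compliance will be calculated for each participant completing the three-week observational period in Stage 2") that compliance is limited to completers. The outcome-measure cell beside it has no such limit, and Protocol 8.5 says compliance "will be assessed at the end of the three-week study period by Closed Loop Medicine", which is a statement of timing.
- A reader might infer from SAP 2.4, which numbers Stage 2 days from the first completed entry, that earlier blank days are not counted. The compliance formula in SAP 3.3 divides days completed by 21 and does not use those day labels, so this is not established. The Day 0 diary baseline in SAP 2.3 affects no compliance measure.
- A reader might treat all 25 planned losses as no-data consenters, giving 125/100 = 1.25. The 25 come from an eligible count and may include people who did not consent or who left partial data.

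**Conclusion.** The concern holds in conditional form. If Stage 2 data means questionnaire or diary data, all three compliance rates are conditional on having given something, and consenters who never engaged are not counted as failures. If site-entered history or the adverse event call counts, the exclusion is nearly empty. It would go too far to say that the plan certainly overstates compliance, or that it reports only on people who engaged, because the open example leaves both readings available.

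The size is unknown and may be zero. The factors of 1.04 to 1.09, and the entry figure of 100% against 96% or 92%, rest on 125 consenters, on 5 or 10 of them leaving no data and, for the entry figures, on no questionnaire-only participants. None of these assumptions comes from the documents.

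The outcome is secondary and descriptive, with no success threshold, and the primary prevalence estimate is untouched. The change is still worth making: it removes a possible bias in an outcome about engagement, and the two rates will simply agree if nobody is excluded. The start date of the 21 days is a minor clarification only.

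**What to change.** 1. In SAP 3.3, report entry, completion and overall compliance with all eligible Stage 2 consenters as the denominator, scoring anyone with no entries as 0 of 21, next to the rates on the current Stage 2 set. Keep the Stage 2 set for the sleep outcomes.
2. In SAP 2.2, replace the example with a closed list of what counts as Stage 2 data. Say explicitly whether site-entered history, the adverse event call and a UEQ that is dropped from reporting count.
3. In the disposition summary, separate Stage 2 consenters excluded as ineligible from those excluded for having no data, and note the effect on compliance in SAP section 4.
4. As a minor clarification, state which date starts the 21 days used for compliance.

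The cost is some SAP wording, one extra row or column in the compliance table and a split of an exclusion count. Consent counts are already to be summarised. The published compliance figure may be less favourable.
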